1.0 Definitions

Definitions

Eligible patients: All patients who meet all inclusion criteria and no exclusion criterion.

Consented participants: All eligible patients who have completed the consenting process.

Enrolled participants: All participants who have been randomized.

Intention-to-treat (ITT) Population: All enrolled participants, regardless of whether they received study drug or completed study procedures. This is the primary analysis population.

Study day: The calendar day of enrollment (randomization) is study day zero. The next day is study day one, and so on.

Assessment day: This corresponds to the survey instrument (day one survey is given on assessment day one).

Study Drug Discontinuation: Participant chooses to discontinue study drug, for any reason. Other study procedures may continue as decision of participant.

Study withdrawal: Participant discontinues study drug and does not wish to provide further study samples or data. Data recorded up to the time of withdrawal will be included in the study analysis.

Serious unexpected suspected adverse event (SUSAR): A serious adverse event or drug reaction that is unexpected and believed related to participation in study.

UTAH One (Understanding Treatment And Health in the Ongoing coroNa Epidemic): A Hydrochloroquine Outpatient Study

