2.5 Inclusion criteria

Inclusion Criteria for Randomized Group:

- Patient age ≥ 18 years, competent to provide consent
- Within 72 hours of positive nucleic acid test for SARS-CoV-2

Inclusion Criteria for Household Contact Group:

- Individual age ≥ 18 living in the same house as someone diagnosed with COVID, competent to provide consent

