2.6 Exclusion criteria

- Patient already prescribed chloroquine or hydroxychloroquine
- Allergy to hydroxychloroquine
- History of bone marrow or solid organ transplant
- Known G6PD deficiency
- Chronic hemodialysis, peritoneal dialysis, continuous renal replacement therapy or Glomerular Filtration Rate $< 20\text{ml/min}/1.73\text{m}^2$
- Known liver disease (e.g. Child Pugh score $\geq B$ or AST >2 times upper limit)
- Psoriasis
- Porphyria
- Known cardiac conduction delay (QTc $> 500\text{mSec}$)
- Concomitant use of digitalis, flecainide, amiodarone, procainamide, propafenone, or any other prescription medication known to prolong the QT interval
- Seizure disorder
- Prisoner
- Weight $< 45\text{kg}$
- Inability to follow-up – no cell phone or no address or not Spanish or English speaking
- Receipt of any experimental treatment for SARS-CoV-2 (off-label, compassionate use, or trial related) within the 30 days prior to the time of the screening evaluation
- Patient or another member of patient's household has been already enrolled in this study.
- History of ventricular arrhythmia

2.7 **Sample size:** The study will enroll up to approximately 200 participants in each arm (total 400 participants).

2.8 **Primary Endpoint:**

UTAH One (Understanding Treatment And Health in the Ongoing coroNa Epidemic): A Hydrochloroquine Outpatient Study

- Duration of viral shedding, as defined by time from randomization to the first of two consecutive negative swabs, measured on days 1 - 14.

2.9 Interim Monitoring:

Formal safety review by Data Safety Monitoring Board (DSMB) after 100, 200, and 300 subjects enrolled. No interim efficacy analyses or monitoring.

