4.0 Study population

Ambulatory patients for whom SARS-CoV-2 testing is obtained at University of Utah testing sites after evaluation via telehealth services or by providers in University affiliated clinical facilities.

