Hospitalization within 14 days of enrollment Hospitalization within 14 days: this is a binary outcome which is “yes” if (a) medical chart review (e.g., performed on *DayD28*) reveals a hospitalization from *DayR* to *DayR+13* (inclusive) or (b) a study assessment reports a hospitalization occurring in this span or (c) the subject is known to have died during this span. If a subjects meets none of these criteria, the outcome will assumed to be “no”. If a subject meets none of these criteria but was lost to follow-up before *DayR+13* and chart review is not permitted because of study withdrawal, the outcome will be considered missing.

Persistence of viral shedding on Day 28 The protocol originally specified a secondary outcome of duration of viral shedding for days 1–14 and 28. Because the primary outcome is viral shedding from *DayR + 1* through *DayR + 14*, the secondary outcome of persistence of viral shedding on Day 28 is substituted for duration through Day 28; there is limited precision between Days 15 and 28. The definition of the persistence of viral shedding on Day 28 outcome relies heavily on the Day 28 swab and is limited to those who have a test result for the Day 28 swab or who are not known to have died on or before *DayR + 30* (there is a ± 2 day window for collecting the Day 28 swab). If the Day 28 swab result is known, the result will be used to define the outcome (“yes” if positive, “no” if negative). Otherwise, subjects with a confirmed cessation of viral shedding when considering daily swab results from *DayR + 1* to *DayR + 25*, inclusive (with the requirement for confirmation waived if the latest available daily result in this interval is negative), and a missing Day 28 value will be assumed to be negative on Day 28; otherwise subjects hospitalized on any of the days *DayR + 26*–*DayR + 30* with a missing Day 28 value will be assumed to be positive on Day 28; otherwise, multiple imputation will be performed as described in Section 7.3.3.

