on what percentage of missing values may be imputed with the mean of the corresponding non-missing values. In the absence of such a recommendation from this source, if no more than one of the relevant items are missing for an individual's total, then the average of the individual's observed item scores from the total will be substituted for the missing items to impute the total. If more than one item is missing, the total will be regarded as missing. If the value is missing because the individual is known to be deceased when the assessment was to have occurred, the GAD-7 change since baseline will be post-processed to 22 (i.e., worse than possible for any survivor) after multiple imputation.

- PHQ-9 Total (baseline, 28 days, and 6 months): The 9 items are scored as 0-3 each, producing a total from 0-27.^[5] Several scoring approaches are noted, such as treating missing item scores as 0 to be “diagnostically conservative” or mean-imputing up to 20% of item scores.^[5] Another validation article allowed 2 of the 9 items to be mean-imputed.^[6] The latter approach will be used such that up to 2 items may be mean-imputed. If the value is missing because the individual is known to be deceased when the assessment was to have occurred, the PHQ-9 change in total since baseline will be post-processed to 28 (i.e., worse than possible for any survivor) after multiple imputation.
- Hospital admission by 6 months: this is a binary outcome which is “yes” if (a) the secondary 14-day hospitalization outcome is yes, or (b) any hospitalization, for any cause, is found in either the 28-day or 6-month chart review or from subject self-report, or (c) the subject is known to have died by the time of the 6-month chart review. This is “no” otherwise, assuming an absence of documentation of hospitalization in the medical chart is “no.”
- Mortality by 14 days: all-cause mortality at *DayR+13*
- Mortality by 28 days: all-cause mortality at *DayR+27*
- Hospital admission by 28 days: this is a binary outcome which is “yes” if (a) the subject self-reported a hospitalization beginning between *DayR* and *DayR+27* inclusive, or (b) 28-day chart review discovered a hospitalization in this interval, or (c) the subject is known to have died during this interval.

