- Post-randomization hospitalizations on or before day of study drug delivery (truncated at *DayR + 13*): this outcome will be assessed for the entire ITT population. This is “yes” if a hospitalization (or death) is documented to have occurred after the time of randomization and *on or* before the earlier of the day of drug delivery (*DayD1*) or (*DayR + 13*). This is “no” otherwise, assuming an absence of documentation of hospitalization/death in the medical chart is “no.”

Subgroup Variables Age group will be determined based on the individual's age at randomization. The age groups will be 18–44, 45–59, 60–74, 75+.

Presence/absence of comorbidity The analysis and/or imputation models of some outcomes utilizes a dichotomous comorbidity variable. Presence/absence of comorbidities will be defined as “Yes” if any of the following are indicated on the medical history form (and “No” otherwise, including if status is not available):

- Diabetes mellitus
- Hypertension
- Chronic pulmonary disease
- Immunocompromised status
- Cardiovascular disease
- Congestive heart failure
- Chronic kidney disease
- Active malignancy
- Cerebrovascular disease
- Chronic liver disease
- Morbid obesity
- Chronic neurological disease

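### The 14-day hospitalization outcome counts admissions from the calendar day of randomization without requiring them to follow assignment, and no eligibility criterion rules out a patient already in hospital.

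*SAP*

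**What the plan says.** **Outcome.** SAP 5.4 gives three routes to a yes for 14-day hospitalization: chart review "reveals a hospitalization from *DayR* to *DayR+13* (inclusive", a study assessment reporting a hospitalization in that span, or a known death in it. SAP 7.3.1 compares the proportions with a CMH test stratified by age, two-sided at 0.05, and presents relative risks.

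**Neighbouring outcomes.** The same SAP section limits the pre-drug hospitalization outcome to cases where "a hospitalization (or death) is documented to have occurred after the time of randomization". For hospital admission by 28 days, the self-report route requires that "the subject self-reported a hospitalization beginning between" DayR and DayR+27. The chart-review route for that outcome asks only for a hospitalization in the interval. Hospital admission by 6 months is yes whenever the 14-day outcome is yes, or when either chart review or self-report shows any hospitalization, with no stated start.

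**Eligibility.** Protocol 1.0 makes the listed criteria decisive: "Eligible patients: All patients who meet all inclusion criteria and no exclusion criterion". Protocol 4.2 only refers back to 2.5 and 2.6, and SAP 4.1 and 4.2.2 rely on the same criteria. The population is described in Protocol 4.0: "Ambulatory patients for whom SARS-CoV-2 testing is obtained at University of Utah testing sites".

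**The concern.** The 14-day outcome is meant to show whether treatment keeps outpatients out of hospital. A person admitted before being randomized has already had the event, and assignment cannot change it. If the counting rule accepts such an admission, the numerator in each arm contains events unrelated to treatment.

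The route to such a case is short. Enrolment may follow the test by up to three days ("Within 72 hours of positive nucleic acid test for SARS-CoV-2"), consent is taken remotely, and the pre-randomization steps in Protocol 5.1 and 5.2 are a medication review and a cardiac review. No step is described as a check of hospital status.

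At stake is the interpretation of a secondary outcome that is named in the primary objective (SAP 2.1.1) and is likely to have few events.

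**Working it through.** **Step 1: can a patient in hospital meet the criteria?** The inclusion criteria for the randomized group are two: "Patient age ≥ 18 years, competent to provide consent" and "Within 72 hours of positive nucleic acid test for SARS-CoV-2". Neither concerns hospital status. Of the 17 exclusions in Protocol 2.6, the nearest to setting is "Inability to follow-up – no cell phone or no address or not Spanish or English speaking", which concerns contact and language. Protocol 4.0 calls the patients ambulatory, but in the context of testing and outside the lists that define eligibility. Read literally, someone tested as an outpatient and admitted before randomization remains eligible.

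**Step 2: would the admission be counted?** DayR is a calendar day (Protocol 1.0, SAP 5.4).

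| Admission | 14-day outcome | 28-day, self-report | Pre-drug outcome |
|---|---|---|---|
| On DayR, before assignment | Counted | Counted | Not counted |
| Before DayR, still in hospital on DayR | Open to either reading | Not counted | Not counted |
| On DayR, after assignment | Counted | Counted | Counted |

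The first row is the firm finding. The second depends on whether a hospitalization from DayR means one that starts then or one that is in progress then. The 28-day outcome therefore shares the first problem, and the 6-month outcome inherits both through the 14-day outcome.

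**Step 3: how large could the effect be?** The documents give no power or event rate for hospitalization. Protocol Table 2, the only power table, concerns shedding. It reproduces with HR = exp[(1.960 + 0.842)/√(0.25 × 400 × rate)], from 1.486 at 50% to 1.368 at 80% (stated 1.49 and 1.37), but it does not enter this point. The protocol says only that few participants are expected to be hospitalized.

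Assumptions, none from the documents: a share q of participants in each arm is admitted before assignment and counted; the control risk p among the rest is 5% or 10%; the true relative risk is 0.50. The sample size of 200 per arm is from Protocol 2.7.

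- Counted risk, control: c = q + (1 − q)p
- Counted risk, HCQ: t = q + (1 − q)(0.5p)
- Expected relative risk: t/c
- Power, unstratified: Φ{[(c − t)√200 − 1.96√(2m(1 − m))] / √(c(1 − c) + t(1 − t))}, with m = (c + t)/2

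Example, p = 5%, q = 1% (2 participants per arm): c = 0.01 + 0.99 × 0.05 = 0.0595; t = 0.01 + 0.99 × 0.025 = 0.0348; t/c = 0.58.

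| q | RR, p = 5% | Power | RR, p = 10% | Power |
|---|---|---|---|---|
| 0 | 0.50 | 26% | 0.50 | 48% |
| 1% | 0.58 | 21% | 0.55 | 43% |
| 2% | 0.65 | 18% | 0.59 | 39% |
| 5% | 0.76 | 13% | 0.67 | 31% |

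The risk difference hardly moves: at p = 5% it is 0.025 with q = 0 and 0.99 × 0.025 = 0.0248 with q = 1%. The ratio is what is diluted. With no treatment effect, c = t and the relative risk is 1 for every q.

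**The case against.** The strongest reply is that this is an outpatient trial throughout. The title, objective and hypothesis say so. Study drug is delivered, swabs are self-collected and picked up by courier, household contacts take part, and hospital admission is handled as something that happens during treatment. Investigators contact each patient after the positive test to verify eligibility. Randomizing an inpatient would conflict with all of this. That stands as a reason to expect few cases, but it does not supply the missing limit in the counting rule.

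A second reply concerns stays already under way. Elsewhere, when the SAP means being in hospital on a given day, it says so explicitly, as in the Day 28 shedding rule. The 14-day outcome also feeds one titled as an admission. On that basis the natural reading is a hospitalization that starts in the window. This is a fair argument. A reader might infer that the SAP plainly counts ongoing stays, but the text leaves it open.

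A third reply is that including DayR captures genuine same-day admissions after assignment. That is right, and the fix keeps them.

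A fourth is that chance imbalance in pre-assignment admissions is ordinary sampling error, already covered by the test. That also stands, and it is not counted here as a separate flaw.

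**Conclusion.** The point holds as a defect in the counting rule, with a matching gap in the eligibility lists. A same-day admission before assignment would be scored as an outcome event. A stay already under way might be.

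The consequence is dilution of the relative risk toward 1 and some loss of power in a secondary outcome. It is probably small. Its size cannot be derived from the documents, and the table above is an illustration that rests on assumed values of q, p and the true relative risk. If no counted admission preceded assignment, the result is unaffected.

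Stronger readings are not supported. A reader might infer that the outcome is systematically biased or its type I error inflated. Events that precede assignment are independent of arm, so neither follows. A reader might also infer that inpatients were in fact enrolled; nothing in the documents says so. The primary shedding outcome has its own rule for hospital days and is not the subject of this point.

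**What to change.** 1. In SAP 5.4 and 7.3.1, count only hospitalizations whose admission begins after the time of randomization, using the limit already written for the pre-drug outcome ("a hospitalization (or death) is documented to have occurred after the time of randomization"). Apply the same rule to the 28-day and 6-month hospitalization outcomes. The end of each window is unchanged.
2. Keep every participant in the ITT population, and report by arm how many otherwise-counted hospitalizations began before assignment.
3. Where only the date of a DayR admission is known, show the result with and without those cases. The documents do not say that chart review records admission dates or times, so this has to be checked first.
4. Label the change post hoc and present both versions. The current SAP postdates the end of enrolment and the viewing of results (its change log for Versions 1.3 and 1.4), and SAP 1.2 requires unplanned analyses to be identified.
5. State outpatient status at randomization in Protocol 2.5 or 2.6, to agree with 4.0. For participants already enrolled this only documents the intended population and cannot change who was randomized.

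The cost is a short SAP amendment, one criterion line, a check of admission times for DayR cases, and possibly a slightly lower event count.

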Six months after enrollment, study staff will verify subsequent hospitalizations and vital status of the participant.

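### The 28-day hospital admission outcome cannot count an in-window admission that only the six-month chart review finds

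*SAP*

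**What the plan says.** SAP 5.4 defines three hospitalization outcomes whose time windows are nested, each with its own list of accepted sources.

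- **14 days (DayR to DayR+13).** The first route opens "medical chart review (e.g., performed on" and then gives DayD28, so the day-28 review is an example. The second is that "a study assessment reports a hospitalization occurring in this span". The third is death.
- **28 days (DayR to DayR+27).** Yes if "the subject self-reported a hospitalization beginning between" DayR and DayR+27, or if the "28-day chart review discovered a hospitalization in this interval", or if "the subject is known to have died during this interval".
- **Six months.** Yes if "the secondary 14-day hospitalization outcome is yes", or if an admission for any cause "is found in either the 28-day or 6-month chart review or from subject self-report", or on death.

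Protocol 5.5 provides the later source: at six months, "study staff will verify subsequent hospitalizations and vital status of the participant".

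SAP 7.5.1 has the 28-day outcome analyzed in the same way as the six-month outcomes. That aligns the analysis method and leaves the accepted sources as they are.

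**The concern.** The six-month definition has two devices that the 28-day definition lacks: it names the later chart review, and it inherits a yes from the shorter window. Without them, an admission whose date is known to lie inside the 28-day window can be left out because of when its record was found. Nested outcomes should also be monotone within a participant: a yes at 14 days should imply a yes at 28 days.

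The outcome is compared between arms by relative risk, and the omission can only remove events. Independent dual programming (SAP 5.5) would not reveal it, since two programmers who follow the text would both leave the event out.

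Capture in the second half of the window is also thinner. Daily assessments, which ask about hospitalization, end on assessment day 15 (Protocol 5.5), and adverse events are recorded only to day 14 or hospitalization (Protocol 8.1). Later admissions depend on the participant's report and one chart review.

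**Working it through.** The plan states no figure here, so the check is of the definitions' logic.

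**Rules.** For a non-fatal admission on DayR+d, let S be a participant report made at any time (study assessments are treated as participant reports), C28 a finding at the 28-day chart review, and C6 a finding at the six-month chart review.

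- 14-day, wide reading (any chart review): d ≤ 13 and (S or C28 or C6)
- 14-day, narrow reading (28-day review only): d ≤ 13 and (S or C28)
- 28-day: d ≤ 27 and (S or C28)
- Six-month: 14-day yes, or S or C28 or C6

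**Enumeration.** Two dates (d = 5 and d = 20) times 2 × 2 × 2 sources give 16 cases. Twelve are yes at 28 days, two are documented nowhere, and two are documented in the window but not counted at 28 days:

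| Admission, found only by C6 | 14-day, wide | 14-day, narrow | 28-day | Six-month |
|---|---|---|---|---|
| d = 5 | yes | not yes | not yes | yes |
| d = 20 | not yes | not yes | not yes | yes |

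On either reading of the 14-day rule both admissions are lost at 28 days. The 14-day/28-day contradiction arises only for d = 5 on the wide reading.

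**Could totals reverse?** Suppose (assumed numbers) 10 admissions fall in the 14-day window and all count there, L more fall in the rest of the 28 days, and a share f of all of them is found only at six months. The 28-day count is (10 + L)(1 − f), which is below 10 only if f > L/(10 + L).

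- L = 0: f > 0
- L = 2: f > 2/12 = 16.7%
- L = 5: f > 5/15 = 33.3%

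**Size of one miss.** Assume that 3–5% of 400 are admitted within 28 days: 400 × 0.03 = 12 to 400 × 0.05 = 20 events. One miss is then 1/12 = 8.3% to 1/20 = 5% of events. With an equal split (6 or 10 per arm of 200), a relative risk of 1 moves to 5/6 = 0.83 or 9/10 = 0.90 if the miss is in the numerator arm, and to 6/5 = 1.20 or 10/9 = 1.11 if it is in the other arm.

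For comparison, the 95% interval is exp(±1.96 × √(1/a − 1/200 + 1/b − 1/200)). For 10 vs 10 the root is √0.19 = 0.436, giving 0.43 to 2.35. For 6 vs 6 it is √0.3233 = 0.569, giving 0.33 to 3.05. One miss lies well inside either interval.

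**The case against.** The best defense is that the uncounted path is narrow. The self-report route has no limit on when the report is made, so an in-window admission that the participant mentions at six months still counts. The 28-day review is also reasonably timed: SAP 5.4 expects DayD1 = DayR+1, so DayD28 = DayR+28, the day after the window closes, and a review then can cover all of it. The loss needs both sources to fail. This stands. A reader might infer that any admission surfacing at six months is dropped; the definition does not support that.

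A reader might also infer that 14-day totals will exceed 28-day totals. That needs the wide reading of the 14-day chart review, although SAP 5.4 names the six-month review explicitly where it intends it. It also needs early six-month-only admissions to outnumber the captured admissions from the rest of the window. The documents support a possible inconsistency in one record and no more.

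Nor does the heading of SAP 7.5.1, which calls these safety outcomes formal, make this a confirmatory endpoint. Its text calls them exploratory, and the analysis it borrows from SAP 7.4.2 and 7.4.3 reports frequencies and relative risks with intervals and specifies no test.

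Finally, it can be argued that a 28-day outcome should rest on 28-day sources, since six-month follow-up runs late and depends on retention. This is weaker. The remedy counts only admissions dated inside the window, and the six-month review may add knowledge without changing the interval. What remains of the argument is that the variable is finalized later.

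**Conclusion.** The point holds as a small defect of definition. By its stated routes, the 28-day outcome excludes an admission dated DayR to DayR+27 that was never reported by the participant, was missed at the 28-day review, and was found by the six-month chart review. No other section of either document repairs this. If the 14-day rule admits chart reviews after day 28, the same participant can also be yes, not yes and yes at 14 days, 28 days and six months when the admission falls by DayR+13.

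The documents give no share of admissions found only at six months, so the overall effect cannot be computed and is probably small. Under the assumed 3–5% admission rate, each miss would be 5–8% of events. The direction is certain: the rule can only undercount.

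**What to change.** In SAP 5.4, define hospital admission by 28 days as yes if the 14-day outcome is yes; or if any study assessment, self-report or chart review (28-day or six-month) documents an admission dated DayR to DayR+27; or if the participant died in that interval. In the 16 cases above, this leaves no 14-day yes without a 28-day yes and no in-window admission found at six months uncounted.

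In the same edit, state when the outcome is no and when it is missing. The six-month definition has an explicit rule for no and the 14-day definition has one for missing; the 28-day definition has neither.

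The cost is a sentence or two and a reprogrammed variable. No new data collection is needed, assuming that the six-month review records admission dates. The downside is that the variable is not final until that review is complete, so any earlier report should be marked as based on the sources available at that time. The SAP's change log shows that the primary manuscript had been drafted before Version 1.4, so a change made now should be labeled post hoc, with the count under the present definition shown beside it.
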